Given the in vitro performance of this novel, fiber-like hydrogel, it is therefore hypothesized that the device may be of benefit in patients with CIC and IBS-C, however, analysis of how it affects whole gut motility has not been conducted. This will be observed using wireless motility capsule (WMC) testing, a non-invasive diagnostic tool capable of measuring intraluminal pressure and pH through the whole GI tract, assessing both transit and contractility. WMC has been demonstrated as a safe, convenient, and reliable method of assessing whole gut transit after a dietary intervention in a more physiologic setting than traditional manometry or scintigraphy.

II. Specific Aims

This is a single center, randomized, double-blind, parallel-group, placebo-controlled pilot study. The purpose of the study is to evaluate the efficacy of the hydrogel capsule CSP01 vs active control (carboxymethylcellulose) vs placebo in accelerating colonic motility among patients with chronic idiopathic constipation. Patients who meet the Rome IV criteria for CIC or IBS-C and who meet the inclusion criteria will be offered participation in this study.

III. Subject Selection

This study aims to recruit 53 total subjects to be enrolled at one site, Massachusetts General Hospital. The 53 subjects that this study aims to recruit factors in a dropout rate of 15%, with a final sample size of 45 subjects.

INCLUSION/EXCLUSION CRITERIA:

Inclusion

1. Age 22-70 years old
2. BMI >18.5 and <35 kg/m²
3. Rome IV criteria for functional constipation or IBS-C
4. Continued IBS-C or CIC throughout Run-in period
5. Compliant with reporting during Run-in (confirm the presence of constipation during the 7-day Run-in baseline period; patients are required to report an average of <3 continuous spontaneous bowel movements [CSBMs] and ≤6 spontaneous bowel movements [SBMs] per week via the interactive web response system).

6. Ability to follow verbal and written instructions
7. Ability to record daily bowel habits, including frequency, stool consistency (BSFS), straining (EoPS), completeness of evacuation, and Patient Reported Outcomes (PROs) (abdominal discomfort, severity of constipation, bloating, overall relief)
8. Informed consent form signed by the subjects

Exclusion

1. History of loose stools
2. History of irritable bowel syndrome with diarrhea (IBS-D) or mixed irritable bowel syndrome (IBS-M)
3. Non-compliance with reporting during Run-in

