In addition to patients of MGH, subjects from the general greater Boston population will also be recruited. Subjects from the general population will be recruited through online advertisements run using the Galen Recruitment Service. Through this service, respondents will be filtered by qualifying questions. Contact information for qualified respondents will be provided to research study staff.

IV. Subject Enrollment

a.) Methods of enrollment

1. Patients may be approached by a research coordinator in the Neurointestinal Health clinic if they have a history of chronic constipation and agree to hear more about the trial
2. Patients may be called by the research coordinator prior to their appointment and asked if they would like to hear more about the trial
3. Any patients agreeing to hear more about the trial will learn more before beginning the informed consent process should they agree to participate as well as determining whether they meet all of the inclusion criteria
4. Patients may be contacted about the research study by their MGH physician on behalf of the research team. Afterward, patients may then be contacted by the research team directly.
5. Subjects who have provided their contact information through internet advertising may be contacted by the research team directly.

b.) Procedures for obtaining informed consent

1. Patients agreeing to participate will sign an informed consent with the study doctor at the time of enrollment, after proper informed consent has been provided by the site.

c.) Treatment assignment and randomization

1. Patients who have been enrolled and consented in the trial will be randomized with a ratio of 1:1:1 with 15 subjects per arm: 15 subjects on 3 capsules BID of CSP01, 15 subjects on 3 capsules BID (morning, evening) of carboxymethylcellulose (CMC), and 15 subjects on 3 capsules BID of placebo (sucrose).
2. We will stratify by Rome IV diagnosis of CIC vs. IBS-C to avoid clustering of IBS-C patients in one group.
3. The study personnel and patients will be blinded to treatment allocation.
4. Patients who fulfill study admission criteria and have a signed consent form will be assigned a 3-digit sequential patient number. The number will be used throughout the study.

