If there is an issue with capsule transit, will be monitored by investigator team and depending on location may exclude patient (i.e. if capsule transit delayed in stomach, would exclude patient based on exclusion criteria of gastroparesis). Patients with no bowel movement for 5 consecutive days, who are in need of a rescue treatment, will be instructed to contact the investigator. The following treatment is recommended, as applicable, in the following order:

- 1. Glycerin suppository
- 2. Enema
- 3. Laxadin/Bisacodyl tablets (3x5mg)

Administration of rescue treatment is at the discretion of the investigator based on an assessment of the subject; administration of rescue should be monitored and recorded.

3. Treatment Period (Day 0 to 22)

- a. **Day 0:** On the visit to initiate treatment, patients will return to the clinic to return their WMC monitor and be treated in a parallel-group design for 3 weeks. At this visit, the patient will return the SmartPill receiver and the study diary. Questions or concerns about the study will be discussed, including any changes in concomitant medications and new or worsening adverse events. If available, results of the SmartPill test will be reviewed by the patient's physician. If it is unclear that the capsule has passed, based on the subject's history or on the study results, erythromycin may be prescribed if the capsule is still in the stomach as a promotility medication or obtain an abdominal x-ray for verification to determine if the capsule is still in the colon. If the subject is female, then a urine pregnancy test will be performed before any abdominal xray. Issues with capsule transit will be addressed as above.

- b. Following the two-week run-in period, subjects will again complete the Rome IV Constipation module confirming that inclusion and exclusion criteria continue to be satisfied, and the patient will be randomized using the IWRS. The IWRS will notify the pharmacy to prepare the study drug (randomization output must only be seen by unblinded pharmacist).
- c. During 3-week treatment period, patients will ingest three capsules, twice daily, before breakfast and dinner (with 16 oz water).
- d. Patients will be asked to refrain from making any major lifestyle changes (e.g., starting a new diet or changing their exercise pattern) during the study.

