This is a randomized, double-blind, single-center clinical exploratory pilot comparing treatment with CSP01 to standard control (CMC) to placebo (sucrose) for prevention of constipation in patients with chronic idiopathic constipation. Notably, there is no data either from the wireless motility capsule or from radio-opaque marker transit studies establishing a clinically-meaningful threshold for change in transit time in response to any colonic motility agent, and our hope is that transit data combined with patient-reported outcomes (our secondary endpoints) from this pilot study would provide a meaningful transit improvement threshold that may be used in future research as well. There is some data demonstrating the effect of dietary fiber on colonic transit time.⁷ If we extrapolate data from the trial of dietary fiber on colonic transit time, which demonstrated a 10-hour difference in colonic transit time with a standard deviation of 12 hours, we would assume the same effect for our standard fiber (CMC) group. Assuming that CSP01 would give an additional 3-hour decrease in colonic transit over conventional fiber, our current sample size would have 94% (with $\geq 90\%$ considered excellent) power to detect a difference. Even with 30 total subjects, we would still have 80% power (see graph below which varies the sample size).

Power Analysis/Sample Size Determination.
For a Repeated Measures Anova with Indicated Specifications, & Assuming
A Test-Retest Correlation of 0.7

If we are more conservative with the effect of CSP01 over standard fiber and decrease the additional effect to 1 hour decreased colonic transit time (1/3 of what

we would expect), we would still have 88% power with our current sample size.

VII. Risks and discomforts

1. Device side effects and adverse events

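### The plan recruits 53 to finish with 45 but randomizes 45, and does not say whether the 15% dropout falls before or after randomization; the stated powers need 45 complete pairs

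*Combined protocol and SAP*

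**What the plan says.** Section III sets the recruitment target: "This study aims to recruit 53 total subjects to be enrolled at one site". It explains that this number "factors in a dropout rate of 15%, with a final sample size of 45 subjects".

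Section IV.c.1 sets the allocation: "Patients who have been enrolled and consented in the trial will be randomized with a ratio of 1:1:1 with 15 subjects per arm". It then lists 15 subjects for each of CSP01, CMC and placebo, 45 in all.

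Section V.a places randomization on Day 0, after consent, a two-week run-in, a baseline wireless motility capsule test and a second eligibility check: "Following the two-week run-in period, subjects will again complete the Rome IV Constipation module confirming that inclusion and exclusion criteria continue to be satisfied". A patient can leave in this interval. For example, "if capsule transit delayed in stomach, would exclude patient based on exclusion criteria of gastroparesis". The second capsule test starts on Day 15 and the monitor is returned on Day 22.

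Section VI.4.b compares colonic transit time (CTT) before and after treatment, in pairs, by a 3x2 repeated measures ANOVA. Section VI.4.a makes all randomized patients the primary efficacy population.

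Section VI.4.c says "our current sample size would have 94" percent power if CSP01 adds 3 hours to the CMC effect. It gives 88% if CSP01 adds 1 hour, and 80% for 30 subjects in the 3-hour case. It does not say there what number the current sample size is.

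**The concern.** A dropout allowance protects the primary analysis only if it covers the losses that remove patients from that analysis. Here a patient needs a CTT before treatment and another on treatment. Anyone who withdraws between Day 0 and Day 22, or has no usable second capsule test, contributes no pair. Analysing all randomized patients does not repair this, because the readable text gives no method for missing CTT.

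Section III treats 45 as what remains after dropout. Section IV.c.1 treats 45 as what is randomized. If the second is followed, nothing is held in reserve for loss on treatment. The web-based randomization system, the pharmacy supply and the intention-to-treat denominator all need one number, and study staff could defend stopping at 45 or at 53.

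**Working it through.** **Inputs.** From VI.4.c: a CMC effect of 10 hours and SD of 12 hours ("demonstrated a 10-hour difference in colonic transit time with a standard deviation of 12 hours"), an added CSP01 effect of 3 hours or 1 hour, and test-retest correlation 0.7. From Section III: 53 recruited, 15% dropout, 45 final. From IV.c.1: 15 per arm. Two inputs are assumed because the readable text does not give them: alpha 0.05, and zero mean change on placebo.

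**1. The dropout arithmetic.** 45 / (1 - 0.15) = 52.9, rounded up to 53; 53 x 0.85 = 45.05. Section III is internally correct. It yields 45 completers only if 15% is taken from 53.

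**2. The stated powers.** In a 3x2 design the group-by-time test is a one-way ANOVA on the change scores.

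- SD of change = 12 x sqrt(2 x (1 - 0.7)) = 9.30 h; variance 86.4.
- 3-hour case, mean changes 0/10/13 h: grand mean 7.67, sum of squared deviations 92.67. With 15 per arm the noncentrality is 15 x 92.67 / 86.4 = 16.09.
- 1-hour case, mean changes 0/10/11 h: grand mean 7, sum of squared deviations 74. With 15 per arm the noncentrality is 15 x 74 / 86.4 = 12.85.

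Power is the noncentral F probability with 2 and N - 3 degrees of freedom:

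| Complete pairs | Case | Recomputed | Stated |
|---|---|---|---|
| 45 | 3-hour | 94.3% | 94% |
| 30 | 3-hour | 79.8% | 80% |
| 45 | 1-hour | 88.2% | 88% |
| 53 | 3-hour | 97.3% | not stated |

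All three stated powers reproduce. The 94% belongs to 45 analysable patients, not to 53.

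**3. What later loss does if 45 are randomized.** At 15% loss after Day 0, 45 x 0.85 = 38.25, about 38 pairs, or arms of 13, 13 and 12. The result depends on which arm has 12:

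| Arm with 12 | 3-hour case | 1-hour case |
|---|---|---|
| Placebo | 88.7% | 80.2% |
| CSP01 | 89.5% | 81.7% |
| CMC | 90.2% | 82.0% |

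Averaged over equal (fractional) arms, 38 pairs give 89.5% and 81.3%. At 39 pairs (13 per arm) the 3-hour power is 90.4%.

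**4. If 53 are randomized.** 53 x 0.85 = 45.05 pairs, which restores about 94% and 88%. By whole arms, 15 / 0.85 = 17.6, so 18 per arm (54) would be needed for equal arms.

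**The case against.** The best defence is that the two sections agree. Consent comes first, and several eligibility criteria can be failed only during run-in: continued constipation, diary compliance, laxative use, loose stools. On this reading 53 are enrolled, about 8 are lost before Day 0, and 45 are randomized 15:15:15. This is a fair reading, and the 15% should not then be applied again.

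A reader might therefore infer too much in three ways:

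- **That following the plan leaves about 38 completers.** The documents apply 15% only to 53, never to 45. The 38 is the outcome if 45 are randomized and the whole 15% falls afterwards.
- **That power drops below the 90% which VI.4.c calls excellent.** At 38 pairs it lies between 88.7% and 90.2%, on either side of that mark. The plan uses 90% as a label, not a requirement.
- **That the plan contains an arithmetic error, or caps the randomization list at 45.** 45 / 0.85 and 3 x 15 are both right. The item on the web-based system gives no list length or stopping rule.

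What the defence does not remove is the gap itself. If the run-in uses up the 15%, no allowance is left for three weeks of dosing and a second capsule test. A further defence, that 15 per arm means the evaluable arms, would make everything consistent, but IV.c.1 says these patients are randomized.

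**Conclusion.** The point holds as an unreconciled figure that the trial relies on. The plan does not say whether 45 is the number randomized or the number analysed, nor when the 15% is lost. Under IV.c.1 as worded, the stated 94% and 88% require no loss of paired CTT after randomization. For later loss between 0% and 15%, power runs from 94% to about 89-90% (3-hour case) and from 88% to about 80-82% (1-hour case).

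The shortfall is modest. Even its low end stays at or above the 80% that the plan cites for 30 subjects, and the study is described as an exploratory pilot. The figures rest on alpha 0.05, zero placebo change, and the plan's own SD and correlation; that all three stated powers reproduce supports these choices. The loss that will actually occur after Day 0 is not given in the documents, so the result is a range.

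**What to change.** Amend IV.c.1 so that 15 per arm is the number with paired CTT, and set the randomization target at 53 in a 1:1:1 ratio (about 18:18:17; 54 if equal arms are wanted). State there and in Section III that the 15% allowance applies after randomization and that run-in failures are not counted in the 53. The text change is a sentence or two and the length of the randomization list. The real cost depends on what the 53 was meant to count: if it counted consented subjects, more than 53 will have to be consented to randomize 53.

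If that is not feasible and randomization is to stop at 45, keep 45 and restate the power in VI.4.c for the expected number of pairs: at 38 pairs, about 90% in the 3-hour case and 81-82% in the 1-hour case. This costs only a revised sentence.

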5. Randomization will be conducted via an interactive web-based response system (IWRS). Based on the randomized treatment assignment, an unblinded pharmacist at MGH will prepare the study treatment in a manner that ensures maintenance of the blind utilizing study-specific labels and completing details pertinent to the individual patient.
6. This is a double-blind study. The individual treatment assignment will not be revealed to patients or their representatives, study staff (except for the unblinded pharmacist), or the sponsor or the sponsor's representatives, until all patients complete the study and the database is locked. The unblinded pharmacist will maintain the treatment assignment for each patient.

V. Study Procedures

a.) Study visits and parameters to be measured

1. Eligibility Screen (Day -28 to -15)

- a. Vital signs, height, weight, and physical exam will be performed.
- b. Rome IV questionnaire to screen for CIC and IBS-C
- c. Blood sample collection (CBC, Chem 7, LFTs, Thyroid Hormone, ESR, and if applicable, serum pregnancy test)
- d. Urine sample for toxicity screening

2. Run-In Period (Day -14 to 0)

Day -14: After a screening visit in which patient eligibility will be determined through use of Rome IV constipation module along with other inclusion and exclusion criteria as above, there will be a two-week run-in period.

During this time no use of contraindicated medication per exclusion criteria or medications that may affect the bowel mobility will be allowed unless the subject has been on a stable dose for the last 3 months:

- a. Laxatives
- b. Prokinetic medications
- c. Anti-Depressant medications
- d. Medications for treatment of Parkinson disease
- e. Opiates
- f. Calcium-channel Blockers
- g. Aluminium/Magnesium
- h. Hydroxides
- i. Chronic use of non-steroidal anti-inflammatory drugs (NSAIDs) as defined by a frequency of at least 3 times a week for at least 6 months. Subjects on cardiac doses of aspirin may be enrolled in the study.

Day -7: Seven days into the run-in period, patients will undergo wireless motility capsule (WMC) testing to assess baseline motility. To allow for complete passing of the capsule, there will be a 7-day period following WMC ingestion prior to initiation of treatment to coincide with the end of the two-week run-in period.

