- e. Patients will be instructed to complete a simple, web-based daily diary using the Redcap system throughout the duration of the study which includes daily recording of number and time of bowel movements, complete/incomplete evacuation, and straining, abdominal discomfort, bloating, constipation severity, and overall relief using a nominal rating scale.
- f. **Day 1:** Subjects will begin taking study device. Patients will complete the Patient Assessment of Constipation Symptoms (PAC-SYM) and Quality of Life (PAC-QOL) to determine the severity of their constipation.
- g. **Day 15:** Following 14 days of treatment, patients will return to the clinic to undergo WMC testing to establish their motility profile on treatment and complete PAC-SYM, PAC-QOL questionnaires.
- h. **Day 22:** Following 21 days of treatment, patients will return to the clinic to return the WMC monitor and complete PAC-SYM, PAC-QOL questionnaires.
- i. **Day 31 (+3 days):** There will be a post-treatment period of 7 days during which time patients will continue to complete their daily diary. The clinical coordinator will call patients at the end of this follow-up period to ensure no adverse events occurred. After completion of the study, patients will be mailed the results of their SmartPill baseline test.

4. Schedule of Events

		Study						
		Run-in period			Treatment period			Post-treatment period
Time Point	Day -28 to -15	Day -14	Day -7	Day 0	Day 1	Day 15	Day 22	Day 31
Eligibility screen	X							
Informed consent	X							
Allocation				X				
CSP01 group				—————				
CMC group				◀	—————			▶
Placebo group				—————				
Rome IV questionnaire	X			X				
Daily diary		X	X	X	X	X	X	X
PAC-SYM		X		X	X	X	X	
PAC-QOL		X		X	X	X	X	
WMC testing			X			X		
Adverse events					X	X	X	X

5. There will be no routine monitoring of labs or imaging for the purposes of the study outside of usual care. Other study monitoring activities will be conducted as per Section IX of this protocol.
6. Patients enrolled in the study will not be allowed to be given standing laxative medications for prophylactic purposes, but rescue medications will be allowed on an as-needed (PRN) basis

b.) Investigational Product (IP) to be used

1. The IP will be supplied by the Sponsor and stored in the MGH inpatient pharmacy
 - a. CSP01 is supplied in capsule form (0.79 g per capsule, 2.37 g per dose)
 - b. CMC dose is supplied in capsule form (0.70 g per capsule, 2.1 g per dose)

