- a. In case of pregnancy, the investigational medical device use must be discontinued and the Sponsor informed. Every effort should be made to follow up the pregnancy until its outcome is available.
- b. The Contract Research Organization (CRO) Clinical Safety will provide the Investigator with the Pregnancy Reporting Form for completion. If the pregnancy is to be terminated, the anticipated date of termination should be provided.

10. Responsibilities of the Investigator

- a. to inform the Sponsor about all AEs
- b. to inform the Sponsor about all SAEs, newly discovered pregnancies or pregnancy outcomes, within 24 h of awareness of the events, by:
 - i. entering the information about the event into the electronic CRF
 - ii. in case the Investigator does not receive an automatic notification from the electronic CRF system of successful SAE submission or electronic CRF data entering is not possible:
 - 1. printing the completed section of the electronic CRF (or in case completion of electronic CRF is not possible, completion of paper SAE form)
 - 2. signing the completed SAE form
 - 3. sending the scanned SAE form by e-mail to the CRO Clinical Safety at [contact] (or in case sending a scan is not possible, faxing it to the CRO Clinical Safety at [contact])
- c. to inform the Sponsor about all device deficiencies
- d. to make every effort to follow up the subject to a satisfactory resolution of the safety event or until the end of the study
- e. to respond to follow-up requests from the Sponsor/CRO Clinical Safety

11. Responsibilities of the Sponsor

- a. to ensure that:
 - i. all AEs are recorded and reviewed with the Investigators
 - ii. all SAEs are reported to the relevant European Regulatory Authorities/Ethics Committees as required by local regulations
 - iii. all suspected USADEs are reported to the FDA/Institutional Review Board as required by the US regulations
 - iv. all device deficiencies are recorded and reviewed with the Investigators
- b. during the course of the study, inform in writing all Investigators about all SAEs occurring at any of the participating sites

- c. to collect and maintain records of all AEs, device deficiencies, and pregnancies

VI. Biostatistical Analysis

[figure not shown]
1. Specific data variables to be collected from WMC
 - a. Colonic Transit Time (CTT), Whole gut transit time (WGTT), Gastric emptying time (GET), Small bowel transit time (SBTT)

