2. Specific data to be collected through patient-reported questionnaires
 - a. Spontaneous Bowel Movement (SBM) frequency rate
 - b. Complete Spontaneous Bowel Movement (CSBM) frequency rate
 - c. Stool consistency (Bristol Stool Form Scale)
 - d. Straining (Ease-of-Passage Scale)
 - e. Abdominal discomfort (Self Assessment on 0–10-point numerical rating scale)
 - f. Bloating (Self Assessment on 0–10-point numerical rating scale)
 - g. Constipation severity (Self Assessment on 0–10-point numerical rating scale)
 - h. Overall relief (Self Assessment on 0–10-point numerical rating scale)
 - i. Balloon Expulsion Time (BET) before and after
 - j. Constipation symptom severity (PAC-SYM)
 - k. Constipation quality of life (PAC-QOL)
 - l. Need for rescue laxatives
3. Study endpoints – As above
4. Statistical methods
 - a. Analysis populations
 - i. Intent-to-treat (ITT) population: all patients who are randomized will be included in the ITT population. This will be the primary population for all analyses of demographics, patient characteristics and disposition, and efficacy data.
 - ii. Safety population: All patients who are randomized and receive any study treatment will be included in the safety population. This will be the primary population for all analyses of safety data
 - iii. Per-Protocol (PP) population: All patients who are randomized and receive the study medication on each day of their hospitalization. Major protocol violations include the following:
 1. Prohibited concomitant medication usage (specifically standing laxatives during hospitalization)The PP population may be used for supplementary analysis of selected efficacy and safety data, as appropriate.
 - b. Endpoint analyses
 - i. Primary endpoint: Colonic transit times will be compared in a paired fashion for individual patients before and after the intervention by means of a repeated measures ANOVA using a 3x2 design to distinguish between the outcomes of the three different groups. We will also use multivariable linear regression to compare change in transit time after adjusting for confounders, specifically: presence of IBS-C, abnormal balloon expulsion testing indicating dyssynergic defecation ($BET \geq 2$ minutes), age, and sex.

ii. Secondary endpoints: The secondary endpoints will be compared in a similar fashion, with logistic regression adjusting for confounders.

c. Power analysis

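### The plan gives no CTT value for a capsule not passed within the 7-day recording; the paired ANOVA would lose the slowest transits and, if treatment works, understate its effect

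*Combined protocol and SAP*

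**What the plan says.** CTT is the single primary endpoint (section V, Data to be collected). It comes from two wireless motility capsule (WMC) recordings.

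- **Baseline, Day -7 to Day 0** (Run-In Period): "To allow for complete passing of the capsule, there will be a 7-day period following WMC ingestion prior to initiation of treatment".
- **On treatment, Day 15 to Day 22** (Treatment Period): "Following 14 days of treatment, patients will return to the clinic to undergo WMC testing to establish their motility profile on treatment". At Day 22, "patients will return to the clinic to return the WMC monitor".

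For the baseline capsule, the text allows discretionary exclusion according to where transit is delayed, with the stomach as its only worked example. At Day 0, if passage is unclear, the team may give a promotility drug for a capsule in the stomach or "obtain an abdominal x-ray for verification to determine if the capsule is still in the colon". No CTT value is attached to any of these outcomes. No counterpart exists for Day 15 to 22.

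The primary analysis (VI.4.b.i) reads: "Colonic transit times will be compared in a paired fashion for individual patients before and after the intervention by means of a repeated measures ANOVA", in a 3x2 design, followed by a regression on change in transit time. For the population (VI.4.a.i), "all patients who are randomized will be included in the ITT population". No missing-data, censoring or scoring rule appears. The 15% allowance in section III is described only as dropout.

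**The concern.** A capsule still in the colon when the monitor is handed back is not an ordinary missing value. Its CTT is known to exceed the time already recorded in the colon, so it is among the longest in the trial. A before/after comparison needs two numbers per patient, and this patient has at most one. With nothing else specified, the method selects patients on the outcome after randomization, which conflicts with the stated intention-to-treat population. The adjusted regression on change has the same gap.

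If active treatment shortens transit, on-treatment non-passage is more common on placebo. Removing those patients takes away placebo's slowest transits, pulls the arms together and reduces the number analysed. If the rule is instead chosen after the data are seen, a trial of 45 patients leaves room for that choice to move the result.

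**Working it through.** **Inputs from the plan.** SD 12 h; CMC effect 10 h; CSP01 a further 3 h, so 13 h against placebo; test-retest correlation 0.7 (VI.4.c). 15 per arm (IV.c). Recording of 7 days = 168 h.

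**Assumptions.** Alpha 0.05 (none is stated in the readable text); CTT bivariate normal; 10 h for stomach plus small bowel, so that CTT up to 168 - 10 = 158 h can be recorded. Mean CTT is not given and is varied.

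**Step 1: reproduce the plan's power.** The group-by-time test equals a one-way ANOVA on change scores.
- SD of change = 12 x sqrt(2 x (1 - 0.7)) = 9.295 h (variance 86.4).
- Variance of the means 0, 10, 13 (divisor 3) = 30.89.
- Noncentrality = 45 x 30.89 / 86.4 = 16.09, with 2 and 42 df.
- Power = 94.3%, against 94% stated. The same formula gives 79.8% at N = 30 (stated 80%) and 88.2% for effects 0/10/11 h (stated 88%).

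**Step 2: when does non-passage matter?** Simulated trials, SD 12 h, dropping any patient without both values:

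| Mean CTT | Lost, placebo/CMC/CSP01 | Power | CSP01 vs placebo |
|---|---|---|---|
| 60-100 h | none | 94% | 13.0 h |
| 130 h | 1-2% | 94% | not tabulated |
| 140 h | 10/7/7% | 92% | 12.6 h |
| 150 h | 35/26/26% | 76% | 11.6 h |

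A wider spread brings losses at lower means. With SD 36 h and effects scaled to 0/30/39 h, a mean of 100 h loses 9/6/5% (power 92%, 37.7 h of 39 h), and a mean of 120 h loses 22/15/15% (power 85%, 36.4 h of 39 h).

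**Step 3: one illustration, two readings of the baseline rule.** Put the cut-off at the 80th percentile of untreated CTT, 0.84 x 12 = 10.1 h above the mean. With a 158 h limit this implies a mean near 158 - 10.1 = 148 h. The cut-off applies to both recordings.

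| Baseline non-passers | Lost after randomization | Pairs left of 45 | Power, complete data | Power, dropped | CSP01 vs placebo |
|---|---|---|---|---|---|
| Excluded before randomization | 10.8/1.2/0.5% | 45 - 15 x 0.125 = 43.1 | 95-96% | 90% | 11.8 h |
| Randomized, then dropped | 29/21/20% | 45 - 15 x 0.70 = 34.5 | 94% | 81% | 11.8 h |

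The estimate is the same in both rows because the pairs that survive are the same kind of patient; only their number differs. Placebo's share of the losses is 10.8/12.5 = 86% in the first row and 29/70 = 41% in the second.

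**Step 4: no treatment effect.** With SD 12 h and mean 150 h, losses are about 35% in every arm, the mean difference is 0.06 h and the type I error is 5.4%. There is no bias.

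**The case against.** **No deletion rule is written.** This is correct. The loss follows from a paired method plus silence, and the population is declared to be all randomized patients. But that declaration supplies no value for a patient without a CTT, so the method still cannot use the patient. A mixed model would retain the baseline value, but it would treat the follow-up as missing at random and ignore that it is known to be long.

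**The 7 days were chosen to let the capsule pass.** Also correct, and the Day 0 provisions are conditional. They show that non-passage was contemplated, not that it is expected to be frequent.

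**The rate has no basis in the documents.** This stands and limits the point. At SD 12 h a material loss needs a mean CTT of about 140 h or more.

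**Rescue may end a slow transit first.** The provision triggered by 5 days without a bowel movement falls inside the 7-day window, and laxatives are available on request. A slow transit may then be recorded as a shortened CTT and not be missing. This is a further distortion that the plan also leaves unaddressed; it does not close the gap.

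**Stronger readings.** A reader might infer that losses come mostly from placebo. That holds for on-treatment losses, if treatment works. If baseline non-passers are randomized, their losses are balanced and placebo contributes only about 41% of the total.

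A reader might also cut off only the second recording at 20% of placebo, which leaves about 41 patients, 12.0 h and 85% power. The plan's assumptions do not allow this: placebo does not change, so the same cut-off removes 20% of every arm at baseline.

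Nor can the whole gain from a baseline-adjusted rank analysis be credited to retaining non-passers. Baseline adjustment alone raises power from 94% to 97% with complete data.

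**Conclusion.** The concern holds in a conditional form. The plan has no CTT for a capsule not passed by the end of recording and no handling at all for Day 15 to 22, and its primary method cannot use such a patient. If active treatment shortens transit, the result is attenuation and lost power. If it does not, the comparison is unbiased, so the error runs toward missing an effect and not toward a false one.

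The size cannot be established from the documents. It ranges from nothing at mean CTTs of 60-100 h (SD 12 h) to a loss of about 1.2 h out of 13 h in the illustration, with power of 90% or 81%. Those figures rest on normality, alpha 0.05, an assumed 20% untreated non-passage rate and, to translate that rate into a mean CTT, 10 h of upper-gut time. This is worth fixing because the remedy is cheap, not because a large bias has been shown.

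**What to change.** In VI.4.b.i, before unblinding:

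1. State that a Day 15 to 22 capsule in the colon and not exited by the end of recording is a right-censored CTT, with lower bound equal to the time from colon entry to end of recording, and that the patient stays in the intention-to-treat primary analysis.
2. Analyse on-treatment CTT on arm, baseline CTT and Rome IV stratum by either a censored-data regression or a worst-rank analysis, with the other as sensitivity. Simply setting unexited capsules to the recording limit restores power (93% against 76% when dropped, at SD 12 h and mean 150 h) but not the difference (11.3 h of 13 h), so it is the weaker choice.
3. State how an unexited baseline capsule enters the model, for example at its recorded lower bound with an indicator.
4. Treat a capsule that never reached the colon as missing CTT or as worst rank, and say which.
5. Report non-passage and rescue use during each recording by arm, and add a sensitivity analysis for rescue inside the window.

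The cost is wording and one extra model, with no added patients or visits. The downside is a primary analysis less familiar than ANOVA.
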